6.2 Description of Evaluations

6.2.1 Screening Evaluation

Screening visit – Potential participants will be screened by the coordinator/Study personnel before enrollment to determine eligibility for the RCT portion of the study based on inclusion/exclusion criteria. Subjects will also be screened for fMRI eligibility; *however* if the subject is ineligible for the fMRI, they may still participate in the RCT portion of the study. In general, the consent will be obtained within 4-6 weeks of the screening visit but subjects will be given all the time necessary to decide whether or not they want to participate in the study.

Subjects in the UNMH Urogynecology clinics with UUI who qualify for study entry will be asked whether they are interested in study participation. These subjects will be assured that declining study participation will not affect their clinical care. In addition, women with UUI who contact the UNMH Ob-Gyn research division expressing interest in study participation will have the study explained to them and follow the same procedures as UNMH subjects (see following). Potential subjects will be given a copy of the study consent for their review. Those who are interested will be administered the OAB Awareness tool, a validated measure which screens for presence of OAB, to screen whether or not they are candidates for the study. They will also be instructed how to keep a voiding diary, if this has not already been done, as it is the standard of clinical care for all subjects with UUI. If they ultimately choose to participate in the study, they will be asked to bring the diary with them for Visit 1 (below). The patient will be given the option to schedule Study Visit 1 or given the option to contact the study coordinator to schedule Study Visit 1 at a later date if they are uncertain regarding study participation.

6.2.2 Enrollment, Baseline Visit/Evaluation and Randomization

Enrollment/Consent & Baseline Visit for women in RCT (Day -60 to -1):

Informed Consent Process: Written informed consent will be obtained from each subject at study entry. And will be obtained by the following process:

- 1) Subjects will be asked if they are interested in study participation in a private setting, and if they verbalize interest, a copy of the consent forms will be explained and given to them to review so that they may discuss the study with family and friends.
- 2) The PI or Co-Is will meet with subjects to review the consent form and confirm the subject's understanding of the study and to answer their questions. Subjects will answer screening questions to ensure they are appropriate candidates for the study.
- 3) If subjects state that they are interested in study participation after explanation of the study as noted previously, an appointment will be made for subjects to return to sign the consent and fill out the baseline information and questionnaires.
- 4) If they state that they are not certain, they will be given the study coordinator's contact information so that they can call study personnel if they decide to participate in the study; a study appointment will be made for subjects to return to sign the consent after they contact study personnel.
- 5) At the enrollment appointment, which occurs in a private setting, subjects sign the consent after study personnel are certain that subjects have had appropriate counseling and understanding regarding the study and that the study and consent have been explained to them in a fashion congruent with their medical literacy. Consent will be obtained after screening is performed and will be re-reviewed in the future in the event changes are required. In general, consent will be obtained at the baseline visit. The PI or Co-ls, Study Coordinator(s) or Study Nurse(s) will obtain verbal and written informed consent on one IRB approved consent after explaining study and before collecting any data. Human subject's protection will follow local and national regulations at all times.

Baseline assessments include:

- Questionnaires OABq-SF, ISI, PPBC, PISQ-12, CRADI-8, IBS Module, IC & VAS pain questionnaire
- Voiding Diary
- Demographics form
- Medical history form
- POP-Q examination if one has not been performed during their routine clinical examination

within the last year (Pelvic Organ Prolapse Quantitation Exam, a validated examination recommended by the International Continence Society to standardize quantitation of patients' prolapse)

Arrangements will be made for cystometric testing, Stanford hypnotic susceptibility testing, and fMRI testing (if the subject is willing and without contraindications to fMRI). The expectation question will also be explained to subjects but will not be formally administered until the subject has been randomized to treatment. Adverse events will be tracked and followed up appropriately as noted in the DSMP. Subjects willing to participate in the fMRI study will be screened regarding whether or not they meet criteria for entry into the fMRI study. Subjects who meet criteria and who are willing to participate in the fMRI portion of the study will be scheduled for their fMRI or arrangements will be made to contact the subject to inform them of the date/time of their fMRI. The subjects will be randomized within a month of obtaining the consent.

Enrollment/Consent & Baseline Visit for Normative Controls ONLY participating in fMRI study (Day 0): In addition to the UUI study subjects described previously, a group of women without UUI and without OAB symptoms (also determined by the OAB Awareness Tool screening questionnaire) will be enrolled. This normative group (approximately 30-35 subjects) will keep voiding diaries, answer questionnaires, and undergo urine pregnancy and dipstick testing and cystometric testing followed by performance of an fMRI in order to compare baseline fMRIs in women with and without UUI. The consenting process will be the same as described for the UUI subjects. For this group of women, cystometrics may be performed the same day they are enrolled and fMRI will be scheduled for the following week (if this is not possible, the fMRI should be scheduled within 2 weeks). The procedures will be performed as outlined previously and subsequently in 6.4.3 and 6.4.4.

Baseline Cystometrics

Cystometrics (Day -60 to -1) Cystometric testing (a bladder filling test during which patient sensations are recorded at various volumes and evidence of stress or urgency incontinence recorded) will be performed. Testing includes a urine pregnancy test and urine dipstick. See MOP Chapter "Study Procedures" regarding forms to be filled. If subject chooses to undergo an fMRI, they will have simulation of their fMRI task performed and may have urine and vaginal swab samples collected and stored for possible future analysis (For example, urine may be analyzed for biomarkers and microbiome analysis. See MOP Chapter "Study Procedures" regarding forms to be filled as noted in Section 5.1.

Baseline FMRI

FMRI (Day -60 to -1 for baseline and week 9 for follow-up) will be performed on women willing and able to have fMRI at baseline and follow-up. Testing includes a urine pregnancy test and urine dipstick. Forms to be completed include the fMRI procedure are noted in the "Study Procedures" MOP and has been described in the Protocol Section 5.1.

Other Baseline Tests/Questionnaires

Stanford Hypnotic Susceptibility Testing (Day -60 to week 1) this validated test may be administered by the hypnotherapist any time before the subject receives either their pharmacotherapy or hypnotherapy intervention. Its administration depends primarily on scheduling issues between the subject and hypnotherapist; attempts will be made to couple this testing with any of the subjects' pre-treatment visits (enrollment, cystometrics, fMRI) though the subject may have to come for a separate visit if this is not possible.

Patient Expectation Question (Day 0 and prior to treatment) the subject will be administered this question after randomization and prior to treatment. The question will be explained to the patient at enrollment, but will not be administered until the patient is notified regarding her group assignment by the Research Coordinator or her designee.

Randomization

Randomization to Treatment (Day 0) Subjects will be informed of their randomization to treatment by the Research Coordinator (or her designee if she is absent). Please refer to Statistics Section 9. Randomization will occur within 2-months of Enrollment. Treatment visits will be initiated within one month following randomization with a goal of initiating treatment within 1 week. However, subjects will be given the necessary time to prepare for their upcoming weekly treatment sessions.

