
Visit 2: Cystometry will be performed (see #5 above, Visit 1) Cystometry is a test where subjects have a catheter placed in their bladder, the bladder is filled with sterile fluid and bladder volumes at which sensations of increasing urge to void are recorded. It is part of clinical care to help distinguish between the different types of incontinence. Subjects will be treated with prophylactic antibiotics the day of cystometric testing after documenting absence of allergies to the antibiotics prescribed. Prior to cystometry the subjects will have a urine pregnancy test (if they are premenopausal and have not had a hysterectomy or permanent sterilization) and urine dipstick performed to rule out a urinary tract infection. While the bladder catheter is still in place, subjects may have urine and vaginal swab samples collected and stored for possible future analysis (For example, urine may be analyzed for biomarkers and microbiome analysis). Those who will undergo fMRI will also undergo a brief simulation of the procedure to be performed in the fMRI; their bladders will be filled and emptied and they will rate their urge to void (from 0-10) while this occurs. This will be done in order to decrease anxiety regarding the procedure while in the fMRI scanner. Subjects may undergo hypnotic susceptibility testing (using the validated Stanford C Hypnotic Susceptibility Test) at this time or any time before their 1st intervention treatment.

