Expectation								
Question-								
Follow-up								
Stanford		х	х	х				
Susceptibility								
Test (choices of								
times=x)								
Pregnancy Test			х	х				
Urine Dipstick			х	х				
Cystometry			x					
procedure								
Checklist &								
Cystometry Data								
Form								
fMRI procedure				х				
Checklist								
fMRI Task			x	x				
sheet and urine and			~	~				
vaginal swab sample								
collected and stored								
for possible future								
analysis.								
Incontinence Log &						x	x	x
Med or Hypnotx CD								
logs								
Adverse Events			х	х		х	х	x
	1	1	1	1	1	1	1	1

		[[[(a		[
Assessment &	Treat4	Treat5	Treat6	Treat7	Treat8	fMRI	Followup	Followup	Followup
Evaluation	V6orV7	V7orV8	V8orV9	V9or	V10or	V12	End Tx	6 mo	12 mo
Tools				V10	V11		V11or13		
	Week 4	Week 5	Week	Week	Week	Week	Week 8-10	Mo 6	Mo 12
			6	7	8	9			
Voiding							х	x	х
Diary									
OABq-SF,							х	х	х
ISI, PPBC, PISQ-									
12, IBS module,									
CRADI-8, BPIC									
Expectation									
Question-									
baseline									
Expectation							x	x	x
Question-							~	~	~
Follow-up									
Urine and							x		
vaginal swah							~		
sample									
collected and									
stored for									
nossible future									
analysis									
Incontinence	v	v	v	v	v				
Log & Med or	^	^	^	^	^				
Hypnoty CD									
logs									
Medication or							x	x	x
Hypnoty							^	^	^
Compliance									
Questionnaire									
Adverse Events	v	x	v	×	×	x	x	x	x
Drognonov Tost	^	^	^	^	^	^ 	^	^	^
Pregnancy Test						X			
Urine Dipstick						x			
fMRI						x			
procedure									
Checklist									
fMRI Task						x			
sheet filled and									
urine and									
vaginal swab									
sample									
collected and									
stored for									
possible future									
analysis.									

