The UNMH CTSC biostatistics core will generate the computer randomization scheme for the study. [name] will generate the scheme before enrollment begins and will be blinded to subject allocation after the RCT is initiated; he will have no patient contact, research personnel will not disclose unique patient identifiers to him, and he will remain blinded to patient randomization until study completion. Trial randomization codes will be maintained by the CTSC and [name] (who is uninvolved with study analysis) will have the ability to break the blind. Breaking blinding is planned when all subjects in the RCT (N=152) have completed 12 month follow-up and when data collection and data quality checking have been completed. In the extremely unlikely event that the study is terminated or discontinued early due to excessive numbers of unanticipated and severe AEs determined to be warranted by the DSMB, the blind will be broken earlier than planned. The latter will occur after agreement by NCCAM and the DSMB, in which case the CTSC biostatistics office will be notified and the blind will be broken.

Group assignments will be placed in opaque, sealed envelopes by an individual otherwise unassociated with the study. The envelopes will be opened and subjects will be randomized only after subjects have signed informed consent and completed baseline evaluations. Investigators involved in interpreting fMRIs, investigators participating in the RCT, study personnel performing data entry and the study statistician will be blinded to knowledge of subjects' treatment groups. Investigator blinding will only be breached if a subject suffers an unexpected clinical event and investigator knowledge of the subject's treatment is essential to providing standard of care. Subjects cannot be blinded to treatment interventions as it will be obvious to them whether or not they are undergoing hypnotherapy or taking medications.

9.3 Definition of Populations (ITT versus Per Protocol) Intention to Treat:

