9.6 Data Analyses

Specific Aim 1: Determine whether a mind/body therapy (hypnotherapy) is as, or is more effective and durable, in treating urgency urinary incontinence (UUI) than a non-mind/body treatment (pharmacotherapy)

Statistical Analysis: Improvement between hypnotherapy and controls will be compared at baseline and followup at 2, 6, 12 months. Because of the possibility that a number of subjects may be cured (i.e. report "0" urgency incontinence episodes) at follow-up on voiding diary, we will use a zero inflated Poisson (ZIP) generalized linear mixed model for the analysis and compare groups' urgency incontinence episodes. The ZIP model analysis is proposed because the data are expected to be relatively low counts with the potential of a large numbers of zeroes, particularly at 2 and 6 months, in excess of those allowed by the Poisson. Simple conversion to percent change will not correct the discrete nature of the data ("cures" become 100 percent change rather than 0 UUI count at 2 months), and standard least squares methods will not be appropriate. If there is no inflation at 0, i.e. standard Poisson regression is appropriate, then the associated log-linear model yields percent change as a natural parameter (by exponentiating the group effect). If there is significant inflation at 0, the confidence interval for percent change in the mean will be constructed by combining the two portions of the model with standard error estimated by the delta method, and checked via bootstrap methods. We will be able to derive mean UUI episodes as well as mean % change in UUI episodes following ZIP model analyses. All other parameters, which are normally distributed or continuous variables, will be compared using a linear mixed model analysis. It is unlikely that there will baseline differences between groups, given that this is a randomized controlled trial. If baseline differences between groups are found (e.g. incontinence duration, coexisting illnesses, prior treatment), appropriate variables will be added to the analysis as covariates. We will include pre-treatment patient expectations and hypnotic susceptibility as covariates in the analysis and determine if they are independent predictors of treatment response. We will not exclude subjects based on hypnotic susceptibility to increase the generalizability of our findings. We anticipate subjects' pre-treatment expectations will be an independent predictor of improvement in urgency incontinence & guestionnaire scores (the previously determined sample size is adequately powered to find a relatively small partial R² of .05¹³ between expectations and outcomes). The primary outcome measure will be change in UUI episodes from baseline to follow-up with a between group comparison, and not "cure". However, the term "cure" may be used for secondary analyses. As such, our definition of "cure" will be: absence of UUI episodes recorded on voiding diaries at 2, 6 and 12 month follow-up. Primary analyses will be performed using intention to treat. A per protocol analysis will also be performed; those who did not comply with the study interventions, extensively used other concomitant treatments known to improve UUI (e.g. used other UUI medications, underwent sacral neuro-modulation), or missed multiple treatment sessions will be considered to have been off protocol subjects. Similar analyses will be performed comparing group differences in change in questionnaire scores while accounting for covariates such as pain/interstitial cystitis (based on VAS pain scale and IC questionnaire) or bowel abnormalities (based on the CRADI-8), medical history and demographic variables (based on the medical history and demographic sheets) on the outcomes.

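### The hypnotic susceptibility score may be taken after a woman knows her arm, yet it is to be a covariate in the Aim 1 analysis; the deciding comparison should not adjust for it

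*Combined protocol and SAP*

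**What the plan says.** Section 6.2.2, under other baseline tests, gives the timing and the tester: "Stanford Hypnotic Susceptibility Testing (Day -60 to week 1) this validated test may be administered by the hypnotherapist any time before" the woman receives either intervention. It adds: "Its administration depends primarily on scheduling issues between the subject and hypnotherapist". The preferred route is stated too ("attempts will be made to couple this testing with any of the subjects' pre-treatment visits"), with a separate visit if that fails. In the same section, cystometry and the baseline fMRI are confined to Day -60 to -1.

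Section 3, Visit 2, has the same open end: "Subjects may undergo hypnotic susceptibility testing (using the validated Stanford C Hypnotic Susceptibility Test) at this time or any time before their 1st intervention treatment". Flow Diagram 1 agrees.

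Table 1 in Section 6.1 marks the test at V1, V2 and V3 as alternative times, with no mark at randomisation or the first treatment visit. Section 9.2 says that "subjects will be randomized only after subjects have signed informed consent and completed baseline evaluations".

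On Day 0, "Subjects will be informed of their randomization to treatment by the Research Coordinator", and treatment is to start within one month, ideally within a week (Section 6.2.2). The hypnotherapists are not among the blinded roles listed in Sections 3, 6.2.3 and 9.2.

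Section 9.6, for Aim 1: "We will include pre-treatment patient expectations and hypnotic susceptibility as covariates in the analysis". It then plans to test whether they independently predict response.

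**The concern.** A baseline covariate is safe to adjust for because assignment cannot have affected it. A score taken after disclosure loses that protection. A woman who expects hypnosis and one who knows she will not receive it may respond differently to a hypnosis test, and the tester may know the arm as well. A woman assigned to medication may also have less reason to attend a separate visit for the test, so missing scores could depend on arm.

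If the arms' mean scores differ for these reasons, adjusting for the score moves the between-arm difference on which non-inferiority may be judged. The analysis of susceptibility as a predictor of response would also mix scores obtained under different knowledge. The plan does not limit the covariate to scores taken before allocation, does not name a model without it as the deciding one, and does not say how a missing score is handled.

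**Working it through.** **Timeline.** The plan states no figure for this point, so the main check sets the texts side by side.

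| Source | When the test may be given |
|---|---|
| Section 6.2.2 | Day -60 to week 1, before the first intervention |
| Section 3 (Visit 2), Flow Diagram 1 | Visit 2, or any time before treatment starts |
| Table 1 | V1, V2 or V3 only, all before Day 0 |
| Section 9.2 | Before randomisation, if it counts as a baseline evaluation |

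Disclosure is on Day 0. The first two rows allow a test after it; the last two do not. The plan as written therefore permits a post-disclosure score, and Section 9.6 uses the score without regard to when it was taken.

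**Size, for illustration only.** In a linear model the adjusted difference equals the crude difference minus slope × (between-arm difference in mean score). If a share p of women is tested late and knowledge of the arm shifts their scores by s SD between arms, then

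movement = p × s × b,

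where b is the outcome slope in percentage points per SD of the score.

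Assumed inputs, none in the documents: s = 0.2 to 0.5 SD; b = 3 to 8 points per SD; p = 10% to 30%.

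- Low end: 0.10 × 0.2 × 3 = 0.06 points.
- High end: 0.30 × 0.5 × 8 = 1.2 points.
- Against the 5-point margin of Section 9.2: 0.06/5 = 1.2% and 1.2/5 = 24%.

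**Is the assumed slope plausible?** Section 9.2 states no SD. Its figures imply one through SD = (true difference + margin) / [(1.960 + 0.842) × √(2/n)], at one-sided 0.025 and 80% power:

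- 52 per arm, true difference 9: 14 / (2.802 × √(2/52)) ≈ 25.5 points.
- 60 per arm, true difference 8: 13 / (2.802 × √(2/60)) ≈ 25.4 points.

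If the score explained 5-10% of outcome variance (assumed), b = √0.05 × 25.45 ≈ 5.7 to √0.10 × 25.45 ≈ 8.0 points per SD. With the same s and p, the movement is 0.10 × 0.2 × 5.7 ≈ 0.11 to 0.30 × 0.5 × 8.0 = 1.2 points, inside the range above.

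**Direction.** If knowing the arm raises hypnotherapy-arm scores (s > 0) and higher scores go with better outcome (b > 0), the subtracted term is positive and adjustment lowers the hypnotherapy estimate. Non-inferiority becomes harder to show. If either sign is reversed, so is the direction.

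**Limit of the arithmetic.** It uses a linear percent-reduction scale, whereas Section 9.6 plans a zero-inflated Poisson mixed model.

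**The case against.** The strongest reply is that late testing is an exception. Section 6.2.2 prefers pre-treatment visits and Table 1 marks only those. The score always precedes treatment, so the therapy itself cannot change it. Section 9.2 defines the deciding test as a bound on the difference in means without covariates, so the adjusted model in Section 9.6 may be only a search for predictors. Finally, Section 11.2 says enrolment is complete, so a new window would change no enrolled woman's test.

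Much of this stands. It limits the size and moves the remedy to the analysis. It does not settle which model decides, because Section 9.6 says the covariates go into the analysis and makes no exception for the primary comparison.

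A reader might also infer several stronger points that the documents do not support:

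- **That the test is optional.** Section 3 and Flow Diagram 1 use permissive wording, but it is tied to timing, and Section 6.2.2 says arrangements will be made for the test. Equally, nothing makes it mandatory.
- **That the shift could reach 12-80% of the margin.** The assumed inputs give 0.2 × 3 = 0.6 to 0.5 × 8 = 4.0 points only if every woman is tested late.
- **That women without a score drop out and intention to treat fails.** No section specifies complete-case analysis. Section 9.3 treats missing observations as missing at random and plans multiple imputation as a sensitivity approach; it is silent on missing covariates. Taking a further loss from the 52 per arm would also double count, since that figure already allows for missing data.
- **That the tester is the woman's likely therapist, or that late testing is what exposes medication-arm women to hypnosis.** Several hypnotherapists are described, and the test involves a hypnotherapist whenever it is given.

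**Conclusion.** The concern holds as an internal inconsistency that matters for the analysis. The plan permits a susceptibility score taken after disclosure of the arm and then treats it as a pre-treatment covariate. How many women were tested late is not known from the documents. With 10-30% late and the assumed shift and slope, the adjusted difference moves by about 0.06-1.2 points, or roughly 1-24% of the margin. The most natural direction is against hypnotherapy, so the documents do not support an inference that this would produce a false claim of non-inferiority.

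The expectation question is the more direct case of the same problem. It is also named as a covariate in Section 9.6, and Section 6.2.2 has it asked after disclosure by design. Its effect is not sized here.

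**What to change.** 1. Reconcile Section 3 (Visit 2), Flow Diagram 1, Table 1, Section 6.2.2 and Section 9.2 to one window, Day -60 to -1, before the envelope is opened. This applies to any woman not yet randomised.
2. Because enrolment is reported complete, state before unblinding that the deciding non-inferiority comparison adjusts for neither hypnotic susceptibility nor the expectation question. Section 9.2 keeps the blind until 12-month follow-up and data checks are finished, which leaves room for this.
3. Compare each test date with the randomisation date, and report late and missing scores by arm.
4. Base the susceptibility predictor analysis on scores taken before allocation, with all scores as a sensitivity analysis, and say how missing scores are handled.

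The cost is wording, a date check and slightly fewer women in a secondary analysis. Applying the late-score rule only to that analysis matters: if late scores were set aside while susceptibility stayed in the deciding model, the rule would itself create missing covariates there.
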